The proposed LLLT protocol will use the Biolase Epic X, an InGaAsP diode laser (940nm) using the pain relief handpiece, a device which has received FDA approval (GUDID 00647529002537) for the treatment of pain, muscle relaxation and healing via increased local circulation. The LLLT will be administered to the experimental group at 30 j/cm^2. The laser will be applied extraorally, on the skin overlying the mandible. Application will be for 40 seconds per side, with 10 seconds administered in four places along the jawline, 1 cm apart starting from the gonial angle. The timing would coincide with standard post-operative care, with the first LLLT administration performed on post-operative day 1, prior to the patient's discharge from the hospital. The follow-up LLLT doses would be given at the standard post-op follow-up visits, at one-week intervals, which would be at week 1, week 2, week 3, week 4, week 5, and week 6. Patients will be seen for evaluation at week 8 and again at approximately 20 weeks post-surgery. The control group will follow the same post-op visit schedule, but receive a dummy treatment in which the laser handpiece is moved over the patient's jaw in a similar fashion as the experimental but without laser irradiation.

Nerve function, pain and swelling will be measured according to objective measures. A baseline measurement will be recorded pre-operatively for nerve function and pain. Baseline for swelling will be used from the final measurement at week 8, due to the changes in mandible length caused by the orthognathic surgery. Measurements for each outcome will also be performed on the days for which

LLLT is administered. The individual who performs the assessment will be blinded to the group to which each patient belongs.

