To evaluate nerve function, three tests will be conducted, a two-point discrimination (TPD) test, a hard stimulus test and soft stimulus test. For the TPD test, the patient will be instructed to close their eyes, and a caliper will be placed on the lateral aspect of the patient's chin. The calipers will start at 0 mm and be incrementally opened in .5mm increments, and the first distance felt by the patient as two distinct points will be recorded reported in millimeters. For the soft- and hard- stimuli tests, the lower face will be divided into eight regions, with four symmetric regions per side. Region 1 will be from the skin on the chin at the midsagittal plane laterally 1 cm. Region 2 will be the skin from the edge of Region 1 extending laterally 1 cm. Region 3 will be the skin from the edge of Region 2 extending laterally 1 cm. Region 4 will be the vermillion of the lower from the midsagittal plane to the commissure. The regions will be designated by an "L" for left or "R" for right, plus a number as per the above scheme. Each region will be checked for nerve function via two tests, a cotton-swab test and a two test. During the evaluation, the patient will be instructed to keep their eyes closed. The cotton-swab test will involve the skin in each region being lightly brushed in a 2cm vertical path twice per region, and the patient reporting if they feel the contact. Likewise, the toothpick test will involve the skin being slightly depressed by the edge of a toothpick in three spots separated by 1 cm each per region, and the patient reporting if they feel the contact. The responses will be recorded as positive or negative for soft (swab) or hard pressure (toothpick), by region.

Pain will be reported via use of a visual analogue scale (VAS). The patient will rate the intensity of the pain on each side of the mandible at each visit. The intensity of the pain will be from zero, meaning complete absence of pain, to 10, indicating the maximum amount of pain imaginable.

Swelling will be measured with a soft measuring tape from the tip of the chin to the lower lobe of the ear, bilaterally. The calculation of the swelling index will be done by subtracting the baseline length (from the six-week post-operative visit) to the measured length and dividing the difference by baseline length and multiplying by 100.

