### **Outcomes (primary and secondary)**

In this study, the predictor variable was the use of laser therapy versus placebo treatment after orthognathic surgery on the mandible. The primary outcome variable was neurosensory disturbance recovery by the TPD, hard and soft sensory tests. The secondary outcome variables are pain reduction, as measured by change in VAS, and swelling reduction, as measured by soft-ruler measurement of lower face.

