### **Data analysis**

The primary outcome, change in neurosensory deficit, is measured by the three clinical tests, TPD, soft-stimulus and hard-stimulus. For TPD, the difference between the LLLT group and placebo group at each time point will be compared using an independent t-test, with alpha set at .05. The soft- and hard-stimulus tests for each region will be analyzed at each time point with a chi-square test. VAS pain score and swelling index will be analyzed using independent t-tests for the measurements on each side at each time point, with alpha set at .05. Linear regression will be performed to analyze the relationship of the pain, swelling and nerve tests with age, skeletal class, direction and magnitude of mandibular movement, and inclusion of genioplasty.

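### Three sensory tests are jointly primary and compared at every visit, two of them region by region (153 tests on the natural reading), with no rule for which result answers the primary question

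*Combined protocol and SAP*

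**What the plan says.** Outcomes (primary and secondary) names the three tests together: "The primary outcome variable was neurosensory disturbance recovery by the TPD, hard and soft sensory tests". Data analysis repeats this and gives each test its own comparison.

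- **TPD.** The arms "at each time point will be compared using an independent t-test, with alpha set at .05".
- **Soft and hard stimulus.** "The soft- and hard-stimulus tests for each region will be analyzed at each time point with a chi-square test". No significance level is written for these tests, and the type of chi-square (plain or continuity-corrected) is not stated.
- **Regions.** Under Study Design, "the lower face will be divided into eight regions, with four symmetric regions per side".
- **TPD site.** Study Design says that "a caliper will be placed on the lateral aspect of the" chin, without saying whether one side or both are tested.
- **Visits.** "Measurements for each outcome will also be performed on the days for which" the laser is given, that is, day 1 and weeks 1 to 6. Then "Patients will be seen for evaluation at week 8 and again at approximately 20 weeks post-surgery". The only outcome explicitly tied to a week-8 measurement is swelling: "Baseline for swelling will be used from the final measurement at week 8". Informed Consent describes weeks 8 and 20 as visits added to routine care.
- **Sample size.** An effect of 0.5 with SD 0.5 at 90% power gives just over 22, hence 23 per arm. The test and visit are not named.

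**The concern.** The Hypothesis section asks a directional question, and Sample Size powers it at 90%, so the trial is presented as confirmatory. Yet the plan yields well over a hundred primary p-values and does not say which of them decides. If results are mixed across tests, regions and visits, as is likely with 23 per arm, the same data could be reported as positive or negative. If any nominal p<.05 were taken as a positive primary result, a laser with no effect would look effective more often than the 5% a reader would assume from the stated alpha.

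**Working it through.** **1. The plan's own sample size.** For two means with difference 0.5 and SD 0.5 (standardised difference 1.0), two-sided .05 and 90% power:

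- Normal approximation: n = 2(1.960 + 1.282)² × (0.5/0.5)² ≈ 21.0 per arm, which rounds up to 22.
- Exact t-test solution: 22.02 per arm, which rounds up to 23. This matches the stated figure.
- Power with 23 per arm: 91%.

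The sizing therefore corresponds to one comparison of means at one two-sided .05 level.

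**2. Number of primary tests.** Tests = visits × (8 soft + 8 hard + 1 or 2 TPD).

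| Visits with sensory testing | One TPD value | TPD per side |
|---|---|---|
| 7 (laser days only) | 7 × 17 = 119 | 7 × 18 = 126 |
| 9 (plus weeks 8 and 20) | 9 × 17 = 153 | 9 × 18 = 162 |

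Nine visits is the natural reading: patients are seen at weeks 8 and 20 for evaluation, and Informed Consent treats those visits as added for the study. The pre-operative baseline is not a treatment comparison and is not counted.

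**3. Exact size of one regional chi-square test.** This enumerates two binomials of 23 with the same deficit rate, at an assumed level of .05. Background and Significance quotes deficit rates of 9% to 84.6%, but as rates after surgery; no section gives a rate per region. The 3% row is my assumption, for a region rarely affected. The mean number of false positives among 153 tests is 9 × .05 + 144 × size, which correlation does not change.

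| Regional deficit rate | Size, plain | Size, corrected | Mean false positives, plain | Mean false positives, corrected |
|---|---|---|---|---|
| 3% (assumed) | .0045 | <.0001 | 1.1 | 0.5 |
| 9% | .0413 | .0036 | 6.4 | 1.0 |
| 50% | .0542 | .0260 | 8.25 | 4.2 |
| 84.6% | .0527 | .0111 | 8.0 | 2.0 |

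**4. Chance of at least one p<.05 with no laser effect.** If tests were independent and each had size .05, the chance would be 1 − .95¹⁵³ = 99.96%. Three tests at one visit would give 1 − .95³ = 14.3%. The tests are in fact correlated, so I simulated null trials with 23 per arm and correlated latent normal outcomes. I assumed correlations of .5 to .9 between tests and regions and .7 to .95 between visits, with regional deficit rates from 84.6% falling to 40% down to a flat 3%.

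| Tests counted | Any p<.05, range over settings |
|---|---|
| All primary tests, plain chi-square | about 20% to 99% |
| All primary tests, continuity-corrected | about 10% to 92% |
| TPD alone over visits, one value per visit | about 8% to 30% |

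The two lowest values in the first two rows combine the strongest correlation (.9 and .95) with the 3% rate. With a flat 9% rate and the same correlation, the minimum was about 55% plain and 15% corrected.

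**5. Power under possible remedies** (t-test, 23 per arm, difference 0.5, SD 0.5).

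- One comparison at .05: 91%.
- Alpha divided by three (.0167): 81%; 90% power would need 28.5, so 29 per arm.

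The 91% depends on the planning SD. Using SDs that Sample Size quotes from cited studies, a difference of 0.5 has 88% power at pooled SD √((0.59² + 0.45²)/2) = 0.525, and 18% at √((1.62² + 1.56²)/2) = 1.590.

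**The case against.** Four points can fairly be made for the plan.

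*It never says that one significant result is success.* True. A reader might infer an any-p<.05 rule from the list of tests, but the documents state no such rule, and none that excludes it. The firm defect is the missing decision rule; the percentages show what follows under one permitted reading.

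*The tests are strongly correlated, and many regions may have few deficits.* This stands, and it matters for size. A reader might conclude that a false positive is nearly certain, from the independence figure, or at least 55% likely, from treating 9% as the lowest regional rate. The documents support neither: they give no correlations and no per-region rates, and at an assumed 3% the figure falls to about 20% plain and 10% corrected. It did not fall to 5% in any setting. TPD alone starts at about 8%, so the excess is not large on every count.

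*Sensory testing at weeks 8 and 20 is reasonably clear.* Largely accepted. A reader might infer that it is absent because measurement of every outcome is stated only for laser days. Read with Informed Consent, the documents point the other way, and naming the tests at those visits is a clarification, not a new procedure.

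*Other methods would serve as well.* Also true. A particular rank test, the order of soft and hard, or baseline adjustment are options. One defined primary comparison, or an explicit rule for several, is the requirement.

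**Conclusion.** The point holds. Three jointly primary tests, compared at every visit and for two of them in each of eight regions, come with nothing that says which result answers the hypothesis. The count is 153 on the natural reading (162 with TPD per side) and 119 or 126 if only laser days count. The analysis does not match a sample size built for one comparison of means. That sample-size figure itself reproduces and is not in dispute here.

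The direction of the error-rate concern is secure, conditional on an any-p<.05 reading and on .05 applying to the chi-square tests. Its size is not secure: the ranges depend on correlations and regional deficit rates that the documents do not give, and on which chi-square is meant. They should be quoted as illustrations only. The matter needs correcting before unblinding because, followed as written, the plan leaves the primary error rate uncontrolled.

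**What to change.** Amend Data analysis before unblinding. Study Design keeps assignments blinded until follow-up is complete and data are validated, so the change can still be made credibly. Suggested wording:

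> Primary endpoint: [lead test] at [named visit], one value per patient. The comparison of the arms on this endpoint, at two-sided 0.05, is the only primary comparison. The other two sensory tests are key secondary endpoints at the same visit, each reduced to one value per patient (for soft and hard stimulus, for example, the number of negative regions, 0 to 8). They are tested in the order [second test], [third test], each at 0.05 only if the test before it is significant. Single-region and other-visit comparisons are descriptive, with 95% confidence intervals.

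TPD is a natural lead because it is the only primary test compared by means, as the sample size is, but Sample Size names no test, so the sponsor chooses. The sponsor should also:

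- state that sensory testing is done at the chosen visit;
- state in Study Design whether TPD is taken on one side or both, and if both, use one per-patient value such as the mean.

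**Alternative.** Keep all three tests primary at one named visit, with one value per patient each and alpha divided by three.

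**Cost.** The main option changes wording and leaves 23 per arm, but two declared primary tests move down the order, and single-region and single-visit p-values can no longer be claimed as primary findings. The alternative lowers t-test power from 91% to 81%, so the stated 90% must be restated or 29 per arm planned. Under either option, power for the region-count tests at 23 per arm has not been shown, and the 91% applies only if difference 0.5 and SD 0.5 suit the chosen test and visit. A week-20 primary visit gives longer follow-up but carries late dropout and possible convergence of the arms, since Background and Significance calls these deficits mostly transient.

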### **Hypothesis**

Administration of low-level laser therapy along the skin over the mandibular body of patients who have had bilateral sagittal split osteotomy surgery for correction of the position of the mandible will reduce pain and swelling and improve neurosensory dysfunction when compared to patients who do not receive the laser treatment.

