### **Sample Size**

Published data (13-15) examining the effect of LLLT on IAN functional recovery shows a range of improvement versus placebo. The percentage of recovery shows that the LLLT treatment led to 27.3% (n=30, not split mouth, standard deviation not reported) (13), 13% (n=12, split mouth,  $7.4167 \pm 1.62$  vs  $8.5000 \pm 1.56$ ) (14), and 15% (n= 15,  $5.12 \pm 0.59$  vs  $5.97 \pm 0.45$ ) (15) improvement in sensory function, with . Additionally, one non-placebo controlled study of patients with long-standing documented neurosensory alteration following dental surgery (12) showed 33% improvement over baseline (n=4).

Using these studies, a sample size graph (Figure 1) was plotted in R Stats Package with the effect size versus sample size, with the standard deviation set to 0.5 and power set to 0.9. In order to detect an effect size of 0.5 with a SD of 0.5 at 90% power a sample size of just over 22 is needed. Therefore, 23 subjects per arm is required.

[figure not shown]

Figure 1- Effect size vs. Sample size.

The oral surgery clinic at Jacobi Medical Center treats approximately 50 patients with orthognathic surgery of the mandible annually, and has done so routinely for the last decade. Recruiting 46 patients to participate, even accounting for potential drop outs or failure to follow-up, should prove feasible.

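### Soft and hard stimulus tests, two of the three joint primary tests, are compared between arms only region by region (up to 144 chi-squares), with no per-patient summary, primary visit, success rule or multiplicity control

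*Combined protocol and SAP*

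**What the plan says.** - Outcomes (primary and secondary): "The primary outcome variable was neurosensory disturbance recovery by the TPD, hard and soft sensory tests". The three tests are not ranked, and no primary visit is named.
- Study Design, on recording: "The responses will be recorded as positive or negative for soft (swab) or hard pressure (toothpick), by region". There are eight regions, four on each side. Each region gets two swab strokes and three toothpick contacts, with no rule for mixed answers within a region.
- Data analysis: "The soft- and hard-stimulus tests for each region will be analyzed at each time point with a chi-square test". The .05 level is stated for the t-tests (TPD, pain, swelling) but not for the chi-squares, and continuity correction is not mentioned.
- Study Design, on timing: treatment and measurement fall on post-operative day 1 and weeks 1 to 6. In addition, "Patients will be seen for evaluation at week 8 and again at approximately 20 weeks post-surgery".
- Hypothesis: the laser "will reduce pain and swelling and improve neurosensory dysfunction when compared to patients who do not receive the laser treatment". This is a statement about patients, not regions.
- Data analysis also plans a linear regression of the outcomes, nerve tests included, on age, skeletal class, mandibular movement and genioplasty. Treatment arm is not among the listed terms.
- Sample Size rests on one comparison of means (difference 0.5, SD 0.5, 90% power), which the plan rounds up from just above 22. Its conclusion reads: "Therefore, 23 subjects per arm is required".

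**The concern.** The hypothesis asks whether treated patients regain more sensation. For the soft and hard tests the plan would return a grid of regional p-values and no rule for reading it. It does not say how many regions must differ, at which visit, or on which of the two tests. What counts as success on two of the three primary tests would then be settled after the results are known.

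That can go wrong in two directions. If any region at any visit may count, the false-positive risk is uncontrolled. If a strict correction over regions is added afterwards, a modest gain spread across the lower face may be missed.

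**Working it through.** **1. The plan's own figure.** Two-sample t-test, difference 0.5, SD 0.5 (standardised difference 1.0), two-sided .05, 90% power: n = 22.02, rounded up to 23 per arm, with power .9125 at 23. The plan's number reproduces. It fits a single comparison of a continuous outcome. It does not cover the regional chi-squares.

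**2. Number of chi-squares.** Regions × tests × visits:
- all post-operative visits (day 1, weeks 1-6, 8 and 20): 8 × 2 × 9 = 144
- laser days only: 8 × 2 × 7 = 112

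**3. Expected false positives.** Assumptions, because the documents give none of these: no treatment effect, .05 per test, the same true positive rate in both arms. The size of one chi-square is the sum of the binomial probabilities of all 23-versus-23 tables with a statistic above 3.84. Multiplied by 144:

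| True % positive | Size, uncorrected | × 144 | Size, continuity-corrected | × 144 |
|---|---|---|---|---|
| 50 | .0542 | 7.8 | .0260 | 3.7 |
| 70 | .0497 | 7.2 | .0238 | 3.4 |
| 80 | .0526 | 7.6 | .0168 | 2.4 |
| 90 | .0452 | 6.5 | .0047 | 0.7 |
| 95 | .0164 | 2.4 | .0005 | 0.07 |

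For 112 tests, the uncorrected range at 50-90% positive is 5.1 to 6.1. These expected counts do not depend on the correlation between regions or visits. The Background section describes deficits as mostly transient, so rates near the ceiling are plausible at late visits.

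**4. Does anything else in the plan combine the regions?** The linear regression is the only other analysis that touches these tests. It lists no treatment term and defines no per-patient score, so it does not compare the arms.

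**5. One score per patient against region tests.** Simulated at one visit, 23 per arm, within-patient correlation 0.3-0.7. The score is the number of positive regions out of 8, by rank-sum test. The comparator is at least one significant region with Bonferroni over eight (uncorrected chi-square).

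| Assumed effect | Score | Region tests |
|---|---|---|
| 70% vs 90% in all regions | 68-91% | 44-56% |
| 50% to 80% in 2 of 8 regions | 10-15% | 43-47% |

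The score is better for a diffuse effect and clearly worse for a local one.

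**6. Power if alpha is shared over three tests.** The strictest Holm step is .05/3 = .0167. For one TPD comparison at 23 per arm:
- standardised difference 1.0: 91% at .05, 81% at .0167
- about 0.68: 62% at .05, 44% at .0167

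The 0.68 comes from one study cited under Sample Size: (8.5000 − 7.4167) / √((1.62² + 1.56²)/2) = 1.0833/1.590 = 0.68. It treats the groups as independent, although that study was split-mouth. The other cited study with SDs gives a larger value: (5.97 − 5.12) / √((0.59² + 0.45²)/2) = 0.85/0.525 = 1.62.

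**The case against.** Each regional chi-square uses one response per patient and validly compares the arms for that region. So a reader might infer that the plan has no between-arm analysis of these tests at all, and that would be wrong. What is missing is a combined answer.

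A reader might also infer that a false-positive finding is almost certain, since 1 − .95^144 is 99.9%. That figure needs independent tests, and these are repeated measures on the same patients. Under a simulated model with assumed correlations, the chance of at least one false positive ran from about 2% (continuity-corrected, 95% positive, strong patient correlation) to over 99% (uncorrected, 90% positive, weaker correlation). The documents give neither rates nor correlations, so no single figure can be defended.

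A per-patient count is also partly a preference. It hides which region differs and loses power if recovery is local. Treatment on both sides and a patient-level hypothesis suggest a diffuse effect but do not establish one.

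Finally, a summary for the soft and hard tests alone would not be enough. TPD is also tested at every visit: up to nine t-tests, or 1 − .95^9 = 37% if they were independent. The plan also does not say how the two sides yield one TPD value.

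All of this stands, and it shapes the fix. None of it supplies the missing success rule.

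**Conclusion.** The concern holds for the soft and hard stimulus tests. Two of three joint primary tests are compared between arms only by region and visit, in up to 144 chi-squares, with nothing that turns them into one conclusion.

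The best-supported measure of size is the expected count: about 6.5 to 7.8 false positives among 144 uncorrected tests at 50-90% positive, down to 2.4 at 95%, and lower still with continuity correction. It rests on 23 per arm, no effect and .05 per test, and that last level is itself an assumption for the chi-squares.

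The documents do not support a stated overall error rate, nor the inference that the trial must enrol more patients. The problem can be corrected in the analysis plan and should be corrected before unblinding.

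**What to change.** Amend Outcomes and Data analysis before unblinding:

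1. Name one primary visit that applies to TPD, soft and hard tests alike. All other visits are secondary.
2. Name one lead primary test at that visit and make the other two secondary. TPD is a natural example, because the sample size fits a continuous outcome; state how the two sides give one value per patient. Alternatively, keep all three primary, share .05 over them by Holm, and restate the power under Sample Size.
3. For each of the soft and hard tests, prespecify one comparison per patient, for example the number of positive regions out of 8 by a rank-sum test. State how mixed answers within a region (two strokes, three contacts) are scored.
4. Keep the regional tests as description, or as secondary tests at the primary visit with Holm adjustment, and say whether they are continuity-corrected or exact. This matters most if a local effect is expected.

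**Cost.** No new data or visits. With a lead test, the other two lose primary status, and the plan's 91% power applies to that one comparison at a standardised difference of 1.0. Under Holm, power at the strictest step is 81% at 1.0 and about 44% at 0.68. What is asked for is a restated power, not a larger trial. The count does not locate the benefit and is weak if only a few regions recover, which is why the regional tests should stay as support.

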## Background and Significance

Orthognathic surgery is an essential part of correcting dentofacial deformities. The most common surgery for correcting mandibular deformities is the bilateral sagittal split osteotomy (BSSO). The BSSO was first developed in 1957 by Obwegeser(1), and allowed for anteroposterior correction of the mandible in either a Class II or Class III direction. The BSSO has been modified over time to improve surgical stability and reduce negative post-operative sequelae. Despite the modifications, there are still several potential complications that patients may experience. The most common post-operative complications are pain, swelling and nerve dysfunction.

As with any surgery, pain and swelling are unavoidable, but the extent can be variable. A variety of both pharmaceutical and non-pharmaceutical approaches are generally used to improve pain and swelling, including warm compresses, pressure dressings and analgesics. Physical interventions may reduce swelling, which in turn reduces pain, but are limited in their penetration. Meanwhile medications carry their own potential negative consequences; opioids carry a risk for dependence and neutropenia and non-steroidal anti-inflammatories can cause digestive issues, renal problems.

Nerve dysfunction leading to neurosensory deficits are a relatively common side effect of a BSSO, with literature estimating rates between 9% to 84.6% (2, 3) The inferior alveolar nerve (IAN) runs through the mandibular canal in the body of the mandible, with a branch, the mental nerve, splitting off and exiting the bone at the mental foramen between the first and second premolars. The IAN provides sensation to the gingiva and teeth, while the mental nerve provides sensation to the lips and the chin. During the BSSO, the IAN is necessarily moved and is at risk for either direct or indirect injury, which leads to the neurosensory deficits which are usually transient, but can be permanent in some cases (4-7). Therapy for IAN dysfunction is limited.

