### Participant Recruitment

The patient pool for this study will be drawn from regular patients scheduled to undergo orthognathic surgery at Jacobi Medical Center. Patients who have been cleared for orthognathic surgery already must be in good health and understand the risks of the surgery. The only additional requirements for inclusion are 1) the planned surgery includes bilateral sagittal split osteotomies; 2) patients must be free from pre-operative inferior alveolar neurosensory deficiencies; 3) the patient cannot have an intra-operative

accidental fracture or rupture of the inferior alveolar nerve. The details of the whole orthognathic surgery will be recorded (including maxillary procedure, genioplasty, and direction of positional change of the mandible) but will not alter eligibility for enrolment in the study.

Since 2013, over 30% of the patients treated for orthognathic surgery at Jacobi Medical Center are between the ages of 15 and 18, which is in line with orthognathic surgery in general. As such, the study aims to include these patients in the potential pool of subjects. Because of the significant portion of patients under the age of 18 in general, and their inclusion will allow for age to be examined as a related factor in how healing proceeds. Their inclusion will also allow for an adequate sample size.

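### The primary outcome is recovery from a nerve deficit, but the analysis never uses the day-1 deficit, so any effect on recovery is diluted (not biased) by patients and regions that were never numb

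*Combined protocol and SAP*

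**What the plan says.** The Outcomes section states: "The primary outcome variable was neurosensory disturbance recovery by the TPD, hard and soft sensory tests". The Data analysis section describes the same outcome as a change: "The primary outcome, change in neurosensory deficit, is measured by the three clinical tests, TPD, soft-stimulus and hard-stimulus". Both wordings presuppose a deficit to recover from.

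Eligibility (Participant Recruitment) asks for the opposite before surgery: "patients must be free from pre-operative inferior alveolar neurosensory deficiencies". It also excludes intra-operative fracture or rupture of the nerve. It does not require a deficit after surgery. The only nerve-function baseline named in Study Design is pre-operative, when every eligible patient should be normal.

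For the swab and toothpick tests, "the lower face will be divided into eight regions, with four symmetric regions per side", and "The responses will be recorded as positive or negative for soft (swab) or hard pressure (toothpick), by region". The analysis is then: "The soft- and hard-stimulus tests for each region will be analyzed at each time point with a chi-square test". The TPD analysis is set out as follows: "the difference between the LLLT group and placebo group at each time point will be compared using an independent t-test, with alpha set at .05".

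Study Design has the nerve tests done on treatment days, the first being post-operative day 1. It does not say whether that day's tests come before or after the first laser or dummy application.

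The Background says that "neurosensory deficits are a relatively common side effect of a BSSO, with literature estimating rates between 9% to 84.6" per cent.

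**The concern.** Recovery needs a starting deficit, and the plan defines none. A region that was never numb is positive at every visit. A region that was numb and regained sensation is positive at the later visits. At any one of those visits the chi-square test cannot tell them apart. In the TPD comparison, a patient whose threshold never changed contributes a normal value that leaves the laser little or nothing to improve. The planned regression does not help: its covariates are age, skeletal class, mandibular movement and genioplasty, not the initial deficit.

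What is at stake is the reading of a null result. If a fair share of patients or regions escape a deficit, a laser that helps those with one could show a small average difference. The planned tests alone would not separate an ineffective treatment from a shortage of patients with anything to recover.

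**Working it through.** **Inputs.** From Sample Size: difference 0.5, SD 0.5, power 90%, 23 per arm. From Data analysis: alpha 0.05 and an independent t-test; sidedness is not stated and two-sided is assumed. From Background: deficit rates of 9% to 84.6%.

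**Step 1: the plan's own figure.** The standardised difference is 0.5/0.5 = 1.0. The noncentral t calculation (two-sided 0.05, 90% power) gives n = 22.02 per arm, matching the plan's statement of just over 22 and its rounding to 23. Power at 23 per arm is 91.2%. A one-sided test would need 17.8 and does not match, which supports the two-sided reading.

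**Step 2: dilution.** Let q be the share of patients with a deficit. Assume the 0.5 difference applies to them, zero applies to the rest, and the SD stays 0.5.

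- All patients: difference = 0.5q, standardised difference = q, n = 23 per arm, noncentrality = q × √(23/2).
- Affected only: standardised difference = 1.0, n = 23q per arm, noncentrality = √(23q/2).

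| q | Mean difference, all patients | Power, all patients | Affected per arm | Power, affected only |
|---|---|---|---|---|
| 100% | 0.50 | 91% | 23 | 91% |
| 95% | 0.475 | 88% | 21.9 | 90% |
| 84.6% | 0.423 | 80% | 19.5 | 86% |
| 70% | 0.35 | 64% | 16.1 | 78% |
| 50% | 0.25 | 38% | 11.5 | 63% |
| 9% | 0.045 | 6% | 2.1 | 10% |

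Under these assumptions the affected-only comparison has more power in every row below 100%, because the all-patient noncentrality shrinks with q while the affected-only one shrinks with √q. The 9% row shows the limit of any remedy: with about two affected patients per arm, neither comparison informs.

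**Step 3: how firm the assumptions are.**

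- *Effect size.* Sample Size quotes two differences with SDs: 5.97 − 5.12 = 0.85 and 8.50 − 7.42 = 1.08. If those are effects in affected patients, 0.5 may already allow for dilution (0.5/0.85 = 59% affected; 0.5/1.08 = 46%). With 0.85 and SD 0.5, all-patient power is 99.8% at q = 84.6% and 80% at q = 50%. But the study with the difference of 1.08 has SDs of 1.62 and 1.56; taking about 1.59, power at 23 per arm is 62% before any dilution.
- *SD.* Mixing normal and impaired thresholds would probably widen the spread. If, for illustration, affected controls averaged 1.0 mm above unaffected patients, all-patient power would be 68% rather than 80% at q = 84.6%, and 26% rather than 38% at q = 50%.

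**Step 4: swab and toothpick tests.** For one region, assume that among affected patients 40% of controls and 90% of laser patients test positive at a given visit. The positive rate over all patients is (1 − q) + q × (rate among affected). At q = 50% that is 70% against 95%: the difference falls from 50 points to 25, and power at 23 per arm falls from 97% to 61%. The expected number of negatives is about 23 × (1 − 0.825) = 4 per arm, below the usual minimum of 5 for a chi-square test.

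**The case against.** The strongest reply is that the all-patient comparison is legitimate. The Hypothesis section concerns patients who have had the osteotomy, not patients with a deficit, and Study Design gives laser or dummy from day 1 regardless of sensation. The effect of treating everyone is a proper randomised question. This stands, and it is why that comparison should be kept.

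A reader might go further and infer that the plan is biased, mixing surgical luck with the treatment effect. The documents do not support that. Allocation is random, so the chance of a deficit is balanced in expectation; unaffected patients cause dilution and noise, not bias. Nor does the plan label a never-numb region as recovered. It records positive or negative, and the two histories share one code.

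A reader might also infer that the trial has 6% power, from the 9% rate. That is not supported either. The Background rates carry no time point, test or unit (patient, side or region). The same section says deficits are usually transient and that the nerve is necessarily moved, so the day-1 rate may be well above a later one. At 95% affected the two approaches are almost equal (88% and 90%).

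Finally, day-1 results will exist, so a shortage of deficits could be seen by anyone who looked. True, but nothing commits the trial to reporting or using them. A subset chosen after unblinding, or defined by tests done after the first laser dose, would be weak evidence.

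**Conclusion.** The concern holds as a gap between the stated outcome and the analysis. The trial sets out to measure recovery but compares sensation at each visit in all patients and regions, with no starting deficit. That it covers all patients and regions is inferred from the absence of any restriction.

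The cost is loss of power for the recovery question. If the planned 0.5 applies only to affected patients and the SD stays 0.5, power is about 80% at 84.6% affected and 38% at 50%, against 86% and 63% when affected patients are compared. Those figures rest on an all-or-none split of what is, for TPD, a graded threshold, and on a deficit rate the documents do not pin down. If nearly all patients have a day-1 deficit, the loss is small. The change is worth making because it is cheap and lets the trial answer its own primary question; the all-randomised result is not invalid without it.

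**What to change.** 1. In Study Design, state that the day-1 nerve tests are done before the first laser or dummy application. This makes the deficit a pre-treatment measure, so grouping by it preserves the randomised comparison.
2. In Data analysis, keep the all-randomised comparison as the effect in osteotomy patients overall, and adjust TPD for the day-1 value. This keeps every patient.
3. Add a pre-specified recovery comparison. For swab and toothpick, take regions negative on day 1 and count a turn to positive as success, with a method that allows for several regions per patient. For TPD, take patients whose day-1 value exceeds their own pre-operative value by a margin fixed before unblinding.
4. Report day-1 deficit rates by arm.

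The changes need no new visits or tests, and no new patients to adopt them. The cost is precision: the recovery comparison has fewer patients, and their number is known only after day 1. Having 23 affected patients per arm would mean enrolling 23/0.846, or 28 per arm, at 84.6% affected, and 23/0.5 = 46 per arm at 50%. Without extra enrolment the recovery comparison falls short of 90% power, and if deficits are rare it will be uninformative. Regions that become numb only after day 1 are left to the all-randomised comparison.
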